### 7.2.2 Sensitivity Analyses

A sensitivity analysis for the primary endpoint (1.1) will be conducted by replicating the primary endpoint analysis under each of the following:

- 1. Per-protocol population (PP)
- 2. Imputation of missing data using last-observation-carried-forward (LOCF)
  - $\circ$  As described in section 5.6.1 of this SAP
- 3. Analysis stratified by study site
  - Approximately 31 sites will be used to enroll patients
  - Sensitivity analysis will be performed on each individual site
- 4. Analysis stratified by gender
  - o Male
  - o Female
- 5. Analysis stratified by age group
  - o 18-45 years
  - 46-65 years

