	8. Patients with clinically relevant hepatic impairment			
	9. Patients with sick sinus syndrome, including sino-atrial block			
	10. Patients with second- or third-degree heart block (without a pacemaker)			
	11. Participation in any other interventional drug trial or exposure to other investigational agents within 30 days before Screening (Visit 1)			
	12. Inability to cooperate or any condition that, in the opinion of the Investigator, could increase the patient's risk of participating in the study or confound the outcome of the study			
	13. Patients with conditions that, in the opinion of the Investigator, would prevent a careful adherence to the protocol			
	14. Patients with severe hypotension			
	15. Patients who suffer from shock (including cardiogenic shock)			
	16. Patients treated with Amlodipine 10 mg and Zofenopril (other than 30 mg)			
Clinical Sites Number of Centres	Approximately 28 clinical sites			
List of Countries	Russia, Hungary, Italy			
Study Duration	• Screening Visit 1, (Week -4)			
(specify different	• Run-in period from Visit 1(Week -4) to Visit 2 (Week 0)			
study phases):	• Assessment period from Visit 2 (Week 0) to Visit 4 (Week 8):			
	The overall duration of the study will be 12 weeks.			
	Screening Visit 1, (Week -4): Grade 1-2 hypertensive patients with			
Subject Study	blood pressure [BP] ranging from ≥140/90 mmHg to ≤179/109			
Phases Duration	mmHg) in treatment with any ACE-i or CCBs*, including ZOF 30			
	mg or AML 5 mg (only dosage allowed) for at least one month prior			
	to Visit 1 will be screened for eligibility.			
	Run-in period from Visit 1(Week -4) to Visit 2 (Week 0): eligible			
	patients will enter a 4 weeks run-in period on the same day of the			

Protocol Version 1.0 of 1 23/04/2021

Study Code: : MEIN/20/ZoAm-Hyp/001

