12.5.3 Sensitivity analysis

A sensitivity analysis for the primary endpoint will be conducted by replicating the primary endpoint analysis under each of the following:

- 1. Per-protocol population
- 2. Imputation of missing data using last-observation-carried-forward (LOCF)
- 3. Analysis stratified by study site
- 4. Analysis stratified by gender
- 5. Analysis stratified by age group

Further details of these analyses will be presented in the SAP

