### 5.8 Multi-Center Studies

Approximately 31 study centers will be used to enroll patients into this study. All sites will be pooled and analyzed collectively, except for the sensitivity analysis for the primary efficacy endpoint which is described in section 7.2.2 of this SAP.

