### 7.2 Primary Efficacy Analyses (Endpoint 1.1)

### 7.2.1 Primary Analysis

Endpoint 1.1: Change in mean sitting DBP between Visit 2 (Week 0) and Visit 4 (Week 8).

Endpoint 1.1 will be analyzed using a paired t-test with a type I error rate of 0.05 to test the null hypothesis that the mean change in DBP is 0 mmHg against a two-sided alternative.

The observed values for sitting DBP will be summarized at Baseline (Visit 2) and Visit 4. The change from Baseline to Visit 4 values will be assessed using the paired t-test as described above and will present the mean, SD, min, max, critical t-value, degrees of freedom (df), 95% confidence internal (CI) and p-value. If resulting p-value  $\leq 0.05$ , the null hypothesis will be rejected, and we will conclude that the mean sitting DBP at Visit 4 is significantly different from that at Baseline. Conversely, if p-value > 0.05, then we will

fail to reject the null hypothesis and we cannot conclude a significant difference between mean sitting DBP at Baseline and Visit 4.

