[2] SD = Standard Deviation. CI = Confidence Interval. df = degrees of freedom.

 [3] Visit 4 CFB results are generated using paired t-test with alpha = 0.05 to evaluate if the mean change in diastolic blood pressure (DBP) from Baseline (Visit 2) to Visit 4 is significantly different from 0.
 Source: Listing 16.2.6
 Program Name: XXXX.SAS
 Date: DDMMMYYYY

- Repeat for the following tables:
  - o 14.2.2.2 Summary of Change in Mean Sitting Diastolic Blood Pressure (DBP) from Visit 2 to Visit 4 Per Protocol Population
    - Change column header from "EFF" to "PP"
  - o 14.2.2.3 Summary of Change in Mean Sitting Diastolic Blood Pressure (DBP) from Visit 2 to Visit 4 Using LOCF Efficacy Population
    - Add footnote to statistic column "[4] Missing blood pressure (BP) values that occur after Baseline (Visit 2) are imputed using Last Observation Carried Forward (LOCF)."
  - o 14.2.2.4 Summary of Change in Mean Sitting Diastolic Blood Pressure (DBP) from Visit 2 to Visit 4 by Study Site Efficacy Population
    - Use of SAS #byar/#byval will produce this table separately for each study site within the same output file.
  - o 14.2.3.1 Summary of Change in Mean Sitting Systolic Blood Pressure (SBP) from Visit 2 to Visit 4 Efficacy Population

		All Patier	nts (N=xx)	
Visit [1]	Statistic [2,3]	Male	Female	
Baseline (Visit 2)	n	xx	XX	
	Mean (SD)	xx.x (xx.xx)	xx.x (xx.xx)	
	Median	XX.X	XX.X	
	Min, Max	xx, xx	хх, хх	
Visit 4	n	хх	хх	
	Mean (SD)	xx.x (xx.xx)	xx.x (xx.xx)	
	Median	xx.x	xx.x	
	Min, Max	xx, xx	хх, хх	
Visit 4 CFB	n	хх	хх	
	Mean (SD)	xx.x (xx.xx)	xx.x (xx.xx)	
	Min, Max	xx, xx	xx, xx	
	t-value (df)	x.xx (x)	x.xx (x)	
	95% CI	(xx.x, xx.x)	(xx.x, xx.x)	
	p-value	x.xxx	x.xxx	

Table 14.2.2.5 Summary of Change in Mean Sitting Diastolic Blood Pressure (DBP) from Visit 2 to Visit 4 by Gender (Efficacy Population)

[1] CFB = Change from Baseline.

[2] SD = Standard Deviation. CI = Confidence Interval. df = degrees of freedom.

[3] Visit 4 CFB results are generated using paired t-test with alpha = 0.05 to evaluate if the mean change in systolic (SBP; endpoint 2.1) or diastolic blood pressure (DBP; endpoint 1.1) from Baseline (Visit 2) to Visit 4 is significantly different from 0.

Source: Listings 16.2.4.1, 16.2.6 Program Name: XXXX.SAS

Date: DDMMMYYYY

- Repeat for the following tables:
  - o 14.2.2.6 Summary of Change in Mean Sitting Diastolic Blood Pressure (DBP) from Visit 2 to Visit 4 by Age Group Efficacy Population

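### The plan's only analysis by site repeats the primary t-test in each of about 31 sites of about 7 patients, so it cannot show whether the pooled result is robust to site differences

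*SAP*

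**What the plan says.** - **Primary analysis (SAP 7.2.1).** "Endpoint 1.1 will be analyzed using a paired t-test with a type I error rate of 0.05 to test the null hypothesis" of zero mean change in DBP, two-sided, on the Efficacy population. There is no site term.
- **Site in general (SAP 5.8).** "All sites will be pooled and analyzed collectively, except for the sensitivity analysis for the primary efficacy endpoint". Outside that one sensitivity analysis, site plays no part in any efficacy analysis. The exploratory models (Protocol 12.5.5, SAP 7.4) have a random effect for patient only.
- **The site analysis.** Protocol 12.5.3 lists "Analysis stratified by study site" and leaves the detail to the SAP. SAP 7.2.2 item 3 fills it in: "Sensitivity analysis will be performed on each individual site".
- **The output.** Table 14.2.2.4 repeats the primary table, including t-value, 95% CI and p-value. The programming note says "Use of SAS #byar/#byval will produce this table separately for each study site within the same output file". No row combines the sites.
- **Number of sites.** SAP 5.8: "Approximately 31 study centers will be used to enroll patients into this study". Protocol synopsis: "Approximately 28 clinical sites".

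**The concern.** A sensitivity analysis by site should ask whether the overall conclusion survives when patients at one site are allowed to resemble each other. Repeating the t-test inside each site asks a different question about 31 times, with very little information each time.

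The question is a fair one here. The primary quantity is one mean change in an unrandomised, open-label cohort, so no control arm within a site cancels a site-specific influence on the change. The sites lie in three countries. The COVID-19 provisions in Protocol Section 8 allow home or self-measured blood pressure and say that not every country or site may be affected. At stake are the usefulness of the plan's only site check and, to a lesser degree, the width of the pooled interval.

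**Working it through.** **Inputs from the documents.** N = 216, 90% power, 5% level, assumed change 4 mmHg, SD of the change 10 mmHg, sizing null 2 mmHg (Protocol 12.2, SAP 4.6); tested null 0 (SAP 7.2.1); about 31 sites (SAP 5.8) or 28 (Protocol synopsis).

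**Assumption.** The documents give no ICC for the change in DBP. I show 0.01, 0.05 and 0.10, with equal site sizes unless stated.

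**1. The plan's own figure.** n = (SD × (z for alpha + z for power) / delta)² with delta = 4 − 2 = 2: (10 × (1.645 + 1.282) / 2)² gives 215 after rounding up. The t-distribution gives 216. So 216 reproduces as a one-sided 5% calculation. It treats all patients as independent and has no allowance for site.

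**2. Patients per site.** 216/31 = 6.97; with 28 sites, 216/28 = 7.7. The 216 are patients who start the assessment period, so the average is lower if some lack a Visit 4 value. A site with one evaluable patient gives no t-test.

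**3. One site's test, n = 7.**
- 95% half-width = t(0.975, 6 df) × 10/√7 = 2.447 × 3.780 = 9.2 mmHg.
- Power for a 4 mmHg fall against 0, two-sided 5%, non-central t: 14.6% (12.7% at n = 6, 16.6% at n = 8).
- If the assumed effect held at every site, 31 × 0.146 = 4.5 sites would be expected to reach p ≤ 0.05. A fully consistent effect would look inconsistent.
- If no site had an effect, the chance of at least one p ≤ 0.05 would be 1 − 0.95^31 = 79.6%.

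**4. The pooled interval.** Planned half-width = t(0.975, 215 df) × 10/√216 = 1.971 × 0.680 = 1.34 mmHg. If sites are treated as a sample from a wider population:
- design effect DE = 1 + (6.97 − 1) × ICC
- clustered half-width = t(0.975, 30 df) × 0.680 × √DE
- real size of a nominal 5% test ≈ 2 × (1 − Φ(1.96/√DE))
- implied between-site SD = 10 × √ICC
- t for an observed 4 mmHg fall = 4 / (0.680 × √DE)

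| Assumed ICC | Between-site SD (mmHg) | DE | Half-width (mmHg) | Size | t on 30 df |
|---|---|---|---|---|---|
| 0.01 | 1.0 | 1.06 | 1.43 | 5.7% | 5.71 |
| 0.05 | 2.2 | 1.30 | 1.58 | 8.5% | 5.16 |
| 0.10 | 3.2 | 1.60 | 1.76 | 12.1% | 4.65 |

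The move to 30 df alone takes the half-width from 1.34 to 1.39. With unequal sites (assumed coefficient of variation of site size 0.6) the three half-widths become 1.45, 1.66 and 1.89 mmHg.

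**5. Effect on the conclusion.** Every t in the table is far beyond the 30-df critical value of 2.04. Even at the extreme ICC of 1, an observed 4 mmHg fall gives DE = 6.97, t = 4/(0.680 × 2.64) = 2.23 and p = 0.034.

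**The case against.** A reader might infer that the primary interval is invalid, or that the primary result could be overturned once site is allowed for. The documents do not support either reading.

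- **Inferential target.** The pooled interval is too narrow only if sites stand for a wider population. If inference is to patients at the participating sites, the pooled t-test is not anti-conservative, because its SD already contains the between-site spread. The documents do not state the target. This stands, and makes the point on width conditional.
- **Size of the ICC.** Nothing in the documents shows that 0.05 or 0.10 is realistic. The endpoint is a within-patient change, so constant site differences in level cancel. Protocol 8.1 also standardises measurement: a sponsor-supplied device, the same arm, three sitting readings, trough timing and a fixed morning window. This stands; the 8.5% and 12.1% figures are illustrations. It limits site differences in measurement but does not remove every site effect on the change.
- **No decision rests on a site p-value.** SAP 7.2.1 bases the conclusion on the pooled test alone, so the 79.6% figure describes a display, not an error rate for any claim. The site tables sit beside those by gender and age group as consistency displays, and they do give n, mean, SD and 95% CI. This also stands.

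It remains true that a set of intervals of about ±9 mmHg does not answer whether the pooled result is robust to site, and that the plan has no other analysis that does.

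**Conclusion.** The point holds as a weakness of one sensitivity analysis. On average figures (about 7 patients per site, SD 10), each site test has about 15% power and a 95% CI of about ±9 mmHg, so sensitivity analysis 3 cannot serve its purpose. That conclusion needs no assumption about the ICC. It rests on a derived average, and actual site sizes will vary.

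The effect on the primary analysis is conditional and modest. Only if inference extends beyond the participating sites, and for the assumed ICCs of 0.01 to 0.10, the half-width would be 1.43 to 1.76 mmHg instead of 1.34, and the nominal 5% size about 5.7% to 12.1%. At the planning values the conclusion against a null of 0 would not change. This is a cheap improvement, not a threat to the primary result.

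**What to change.** Keep the pooled paired t-test as the primary analysis. In SAP 7.2.2, replace item 3 with one model of the Visit 2 to Visit 4 change in DBP, with an intercept and a random site effect. Report the intercept, its 95% CI and the between-site SD. Site-clustered standard errors with small-sample degrees of freedom are an alternative; they keep the same point estimate as the t-test, but the between-site SD would then have to be estimated separately. Show site means and 95% CIs in a table or plot, descriptively and without p-values. Align SAP 5.8 and Table 14.2.2.4 with this.

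The cost is SAP wording, one extra model and one shell, with no new data or visits. The analysis remains one by site, as Protocol 12.5.3 announces. The downside is a slightly wider interval in the sensitivity analysis.

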### 7.3 Secondary Efficacy Analyses

The secondary efficacy endpoints are derived from the primary objective and will be used to support the conclusion of the primary efficacy endpoint, provided that the primary efficacy endpoint is met.

All continuous efficacy variables will be summarized for all study visits using descriptive statistics for both actual values and change-from-baseline values. The Efficacy population will be used to analyse the secondary endpoints.

#### 7.3.1 Mean Change (Endpoints 2.1 and 2.2)

Endpoint 2.1: Change in mean sitting SBP between Visit 2 (Week 0) and Visit 4 (Week 8).

Endpoint 2.1 will be analyzed using a paired t-test with a type I error rate of 0.05 to test the null hypothesis that the mean change in SBP is 0 mmHg from Visit 2 to Visit 4 against a two-sided alternative.

**Endpoint 2.2**: Change in mean sitting DBP and SBP between Visit 3 (Week 4) and Visit 4 (Week 8) in patients uncontrolled at Visit 3 and up titrated to the extemporaneous combination of ZOF/AML 30/10 mg.

Endpoint 2.2 will be analyzed using paired t-test for DBP and SBP with a type I error rate of 0.05 to test the null hypotheses of 0 mmHg mean change from Visit 3 to Visit 4 against a two-sided alternative.

### 7.3.2 Proportion of Patients (Endpoints 2.3 and 2.4)

**Endpoint 2.3**: Monotherapy: Number and proportion of patients achieving the BP goal (sitting BP $\leq$ 130/80 mmHg) at Visit 2 (Week 0). Combination therapy: number and proportion of patients achieving the BP goal (sitting BP $\leq$ 130/80 mmHg) at Visit 3 (Week 4) and Visit 4 (Week 8).

**Endpoint 2.4**: Adherence to the treatments (% of doses taken/doses to be taken) at Visit 2 (Week 0), Visit 3 (Week 4) and Visit 4 (Week 8).

Endpoints 2.3 and 2.4 will be analyzed using a 95% binomial confidence interval (CI) for each visit.

A patient who has taken at least 80% and no more than 120% of the required study medication since the last visit will be considered as compliant. Treatment adherence will be summarized incrementally rather than cumulatively so that changes in adherence over time can be accurately reflected. That is, a patient can be compliant between Visits 2 and 3, but non-compliant between Visits 3 and 4, or vice versa.

### 7.4 Exploratory Efficacy Analyses

Each of the exploratory efficacy analyses described in the subsections below will be performed on the following treatment subgroups:

**Test Group**: Patients who were on ZOF 30 mg or AML 5 mg at Visit 1 (Week -4) and continued the same therapies.

**Comparison Group**: Patients who switched to ZOF 30 mg or AML 5 mg from any other ACE-i or CCBs at Visit 1 (Week -4).

### 7.4.1 Mean Change (Endpoints 3.1 and 3.2)

**Endpoint 3.1**: Change in mean sitting SBP and DBP between Visit 1 (Week -4) and Visit 2 (Week 0), Visit 3 (Week 4) and Visit 4 (Week 8).

**Endpoint 3.2**: Change in mean sitting SBP and DBP for uncontrolled patients at Visit 3 (Week 4), between Visit 2 (Week 0) and Visit 3 (Week 4).

Endpoints 3.1 and 3.2 will be analyzed using mixed models for repeated measured (MMRM) to assess the mean change in SBP and DBP. The models will be built as follows:

- Endpoint 3.1
  - *Response* = change from screening BP
  - *Covariates* = treatment subgroup, study visit, treatment subgroup-by-visit interaction, screening BP values
  - *Random effect* = patient
  - Covariance matrix = unstructured
    - In the event of lack of model convergence, other covariance structures may be used.
    - If all MMRM fail to converge, this endpoint will be analyzed as described in section 7.4.1.1 below.
- Endpoint 3.2
  - *Response* = change from baseline BP

- *Covariates* = treatment subgroup, study visit, treatment subgroup-by-visit interaction, baseline BP values
- *Random effect* = patient
- *Covariance matrix* = unstructured
  - In the event of lack of model convergence, other covariance structures may be used.
  - If all MMRM fail to converge, this endpoint will be analyzed as described in section 7.4.1.1 below.

Least-squares (LS) means, standard error (SE), and 95% CIs for mean change from screening/baseline for BP will be presented by visit and treatment subgroup. The LS-means difference, SE, 95% CI, and two-sided p-value for the difference between treatment subgroups in mean change from screening/baseline for sitting SBP and DBP will be presented where a p-value of  $\leq$  0.05 indicates a significant difference between groups.

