Identification Number	Version Number	State	Effective date
FORM-000050125	2.0, CURRENT	Effective	08, Jan 2021

- Study Drug Compliance assessment by return of monotherapy ZOF and AML tablets (also empty blister) and IP accountability
- AEs and serious adverse events (SAEs) assessment
- IWRS update
- Patient's instruction to use the automatic blood pressure device, including patient's diary to be returned at site by the patient

The patients with uncontrolled BP (SBP/DBP >130/80 mmHg), who tolerated the treatment and whose adherence to the therapy ranges from 80% to 120%, will enter the assessment period and at this visit will be dispensed with extemporaneous combination of ZOF 30 mg and AML 5 mg.

To correctly evaluate the additional effect of the combination therapy, the number of patients with uncontrolled BP on AML or ZOF monotherapy needs to be balanced at Visit 2. In order to maintain a 1:1 ratio during the assessment period, a cap of 110 patients for each arm (i.e., AML and ZOF) will be included at Visit 2 in order to maintain a balanced number of uncontrolled patients entering the assessment period for each drug (please refer to section 8 IWRS registration). The evaluation will be done every 50 patients. If the rate of entrance in the assessment period for one of the 2 tested drugs will deviate more than 5%, a corrective measure will be initiated: according to the enrolment site statistics, one or more sites will be informed to enrol a greater number of patients being treated with the least represented drug in the assessment period.

Visit 3 (Week 4 ± 2 days)

The following procedures/assessments will be performed at Visit 3:

- Recording of concurrent diseases and medical conditions
- Concomitant medications
- Vital sign measurements
- Physical Examinations
- BP Measurement
- Urine pregnancy test (UPT)
- Study Drug Compliance assessment (Study Drug Compliance assessment extemporaneous combination of ZOF 30 mg and AML 5 mg) return (also empty blisters) and IP accountability

ИЕМАЯНИ	Corporate Medical Department		
Identification Number	Version Number	State	Effective date
FORM-000050125	2.0, CURRENT	Effective	08, Jan 2021

- AEs and serious adverse events (SAEs) assessment
- IWRS updates
- Patient's instruction to use the automatic blood pressure device, including patient's diary to be returned at site by the patient

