12.5.5 Exploratory (efficacy) analysis

The exploratory efficacy endpoints assessing change-from-baseline BP will be analysed using mixed models for repeated measured (MMRM). The models will include treatment subgroup, analysis visit, treatment subgroup-by-visit interaction, the baseline BP value as a covariate, and patient as a random effect. An unstructured covariance structure was used to model the within-patient errors. The exploratory efficacy endpoint for proportion of patients achieving controlled BP will be analysed using a logistic MMRM with similar terms.

Additional details will be summarized in the Statistical Analysis Plan.

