### 4 Study Methods

### 4.1 General Study Design and Plan

This is a phase IV, open-label, multicenter, multinational study with 2 study periods: a 4-week run-in period and an 8-week assessment period.

Approximately 290 patients are planned to be screened to ensure at least 216 patients complete the run-in period and start with the assessment period.

Patients with Grade 1-2 hypertensive patients (blood pressure [BP] ranging from  $\geq$ 140/90 mmHg to  $\leq$ 179/109 mmHg) on treatment with any angiotensin converting enzyme inhibitors (ACE-i) including Zofenopril 30 mg or with calcium channel blockers (CCBs) including Amlodipine 5 mg will be screened for eligibility (Visit 1).

Allowed CCBs: Felodipine, isradipine, lacidipine, lercanidipine, nicardipine, nifedipine, and nisoldipine. Patients treated with other dosages of Zofenopril (other than 30 mg) are not allowed to be screened.

After screening, on the same day, eligible patients, will enter into a 4-week run-in period, during which patients on other ACE-i will be assigned to monotherapy with ZOF 30 mg while patients on CCBs will be assigned to monotherapy with AML 5 mg for 4 weeks. Patients with on-going treatment zofenopril 30 mg and amlodipine 5mg will continue on the same treatment for 4 weeks.

After the run-in period (4 weeks  $\pm$  2 days), BP will be further assessed (Visit 2), if BP levels are over the defined controlled target goal (sitting SBP/DBP >130/80 mmHg), treatment is well tolerated and adherence to the treatments ranges from 80% to 120%, patients will enter the assessment period, where they will be assigned to the extemporaneous combination of ZOF 30 mg and AML 5 mg. At Visit 2 patients with SBP/DBP values classified as Grade 3 (SBP  $\geq$  180 or DBP  $\geq$  110 mmHg) hypertension will be withdrawn from the study.

If patients, at Visit 2, after the run-in period, have a controlled BP (sitting SBP/DBP≤130/80 mmHg) or do not tolerate the treatment or have an adherence range below 80% or superior to 120%, they will be withdrawn from the study.

The patients will be assessed for further 8 weeks (assessment period).

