#### 7.4.1.1 Model Nonconvergence

If the above MMRMs fail to converge, endpoints 3.1 and 3.2 will be analyzed using independent sample t-tests to compare the mean change in BP in the test group to the comparison group (test/comparison groups defined in section 7.4).

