### 7.4.2 Proportion of Patients (Endpoints 3.3 and 3.4)

**Endpoint 3.3**: Monotherapy: number and proportion of patients achieving the BP goal (sitting BP  $\leq 130/80$  mmHg) at Visit 2 (Week 0). Combination therapy: number and proportion of patients achieving the BP goal (sitting BP  $\leq 130/80$  mmHg) at Visit 3 (Week 4).

**Endpoint 3.4**: Monotherapy: number and proportion of patients divided in subgroup by the hypertension grade, the presence of diabetes and/or of hypercholesterolemia achieving the BP goal (sitting BP  $\leq$ 130/80 mmHg) at Visit 2 (Week 0). Combination therapy: number and proportion of patients divided in subgroup by the hypertension grade, the presence of diabetes and/or of hypercholesterolemia achieving the BP goal (sitting BP  $\leq$ 130/80 mmHg) at Visit 3 (Week 4) and Visit 4 (Week 8).

Endpoints 3.3 and 3.4 will be analyzed using a logistic MMRM to assess the proportion of patients achieving the BP goal (sitting BP  $\leq$ 130/80 mmHg). The models will be built as follows:

- Endpoint 3.3
  - *Response* = achieving BP goal (sitting BP ≤130/80 mmHg)
  - *Covariates* = treatment subgroup, study visit, treatment subgroup-by-visit interaction, baseline BP values
  - *Random effect* = patient
  - Covariance matrix = unstructured
    - In the event of lack of model convergence, other covariance structures may be used.
    - If all logistic MMRM fail to converge, this endpoint will be analyzed as described in section 7.4.2.1 below.

- Endpoint 3.4 by hypertension grade
  - *Response* = achieving BP goal (sitting BP ≤130/80 mmHg)
  - *Covariates* = treatment subgroup, study visit, treatment subgroup-by-visit interaction, baseline BP values
  - *Random effect* = patient
  - Covariance matrix = unstructured
    - In the event of lack of model convergence, other covariance structures may be used.
    - If all logistic MMRM fail to converge, this endpoint will be analyzed as described in section 7.4.2.1 below.
  - Stratification factor = Baseline hypertension grade
- Endpoint 3.4 by presence of diabetes and/or of hypercholesterolemia
  - *Response* = achieving BP goal (sitting BP ≤130/80 mmHg)
  - *Covariates* = treatment subgroup, study visit, treatment subgroup-by-visit interaction, baseline BP values
  - *Random effect* = patient
  - *Covariance matrix* = unstructured
    - In the event of lack of model convergence, other covariance structures may be used.

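### The exploratory continued-versus-switched comparisons leave out run-in drug, so a ZOF–AML difference can enter the subgroup difference if the drug mix is unequal

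*SAP*

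**What the plan says.** SAP 7.4 defines the test group as "Patients who were on ZOF 30 mg or AML 5 mg at Visit 1 (Week -4) and continued the same therapies". The comparison group is patients moved to either drug from any other ACE inhibitor or CCB. Run-in drug follows the class of the previous drug: SAP 4.1 states that "patients on other ACE-i will be assigned to monotherapy with ZOF 30 mg", and patients on other CCBs go to AML 5 mg.

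The Endpoint 3.1 model in SAP 7.4.1 has "treatment subgroup, study visit, treatment subgroup-by-visit interaction, screening BP values" as covariates. Endpoints 3.2, 3.3 and 3.4 use "treatment subgroup, study visit, treatment subgroup-by-visit interaction, baseline BP values". Protocol 12.5.5 has the same structure: "The models will include treatment subgroup, analysis visit, treatment subgroup-by-visit interaction, the baseline BP value as a covariate, and patient as a random effect". Endpoint 3.4 is further stratified by hypertension grade and by diabetes or hypercholesterolemia, but not by drug. If the mixed models fail, SAP 7.4.1.1 uses "independent sample t-tests to compare the mean change in BP in the test group to the comparison group", and SAP 7.4.2.1 uses a binomial interval and odds ratio by subgroup. SAP 7.4.1 and 7.4.2 both read p ≤ 0.05 as a significant difference between the groups.

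On balance, Protocol 5.1 says that "the number of patients with uncontrolled BP on AML or ZOF monotherapy needs to be balanced at Visit 2" and caps each drug at 110 patients there. SAP 4.1 aims for 1:1 by drug class at enrolment. Both targets are overall; neither applies within continued or switched patients.

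**The concern.** In a non-randomized study, pooling two drugs inside each comparison group is harmless only if the mix is the same in both groups or the drug does not matter to the outcome. Nothing in the plan secures the first condition. One split is ZOF 30 mg against any other ACE inhibitor; the other is AML 5 mg against seven named CCBs. The proportion of continuers need not be the same in the two classes.

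The second condition cannot be taken for granted. At Visit 2 the run-in drug is the only study treatment. From Visit 2 everyone takes both drugs, but the run-in drug still fixes which one was newly added.

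These are the plan's only between-group tests; the primary and secondary analyses are paired t-tests or single-proportion intervals. At stake is how a small p-value is read under SAP Objective 3.2, which concerns prior-therapy status.

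**Working it through.** **The plan's own figure.** No sample size or power is stated for these comparisons. The only design figures are those in SAP 4.6 for the primary paired test: 216 patients, SD 10 mmHg, 4 mmHg against a null of 2 mmHg. The normal approximation with one-sided 5% and 90% power gives (10 × (1.645 + 1.282) / 2)² ≈ 214; the t-based calculation gives 216, so the figure reproduces in that one-sided form. It says nothing about continued versus switched. It serves here only as a source for N and the SD.

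**Inputs**
- From the documents: N = 216; SD = 10 mmHg, stated for DBP change from Visit 2 to Visit 4; two-sided α = 0.05 (SAP 5.5).
- Assumed: an even split, 216 / 2 = 108 per subgroup; a drug difference d in BP change of 0 to 4 mmHg; drug shares in the two subgroups from 50/50 to 70/30; no true effect of prior-therapy status.

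**Does the overall cap prevent an imbalance?** No. Take 33 ZOF and 77 AML among 110 continued patients, and 77 ZOF and 33 AML among 110 switched. Each drug totals 33 + 77 = 110, exactly at the cap, while the AML share is 70% in one subgroup and 30% in the other.

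**Formulas**
- Spurious difference b = d × (share in one subgroup − share in the other).
- SE = 10 × √(2/108) = 1.36 mmHg.
- Rejection rate = 1 − Φ(1.96 − b/SE) + Φ(−1.96 − b/SE).

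| d (mmHg) | Shares | b (mmHg) | b/SE | Rejection rate |
|---|---|---|---|---|
| any | 50/50 | 0 | 0 | 5% |
| 0 | any | 0 | 0 | 5% |
| 2 | 60/40 | 2 × 0.2 = 0.4 | 0.29 | 6% |
| 3 | 70/30 | 3 × 0.4 = 1.2 | 0.88 | 14% |
| 4 | 70/30 | 4 × 0.4 = 1.6 | 1.18 | 22% |

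**Check by simulation.** There were 5,000 runs per scenario, with 110 per subgroup and 110 per drug. Each run fitted a single-visit analysis of covariance with subgroup and starting BP, a simplification of the planned mixed model. With 2 mmHg and 40/60 ZOF shares, the mean spurious difference was 0.39 mmHg in size and rejection was 6.2%. With 4 mmHg and 30/70 they were 1.62 mmHg and 20.5%. With equal shares or no drug difference, rejection was 4.8% to 5.7%. Starting BP therefore does not stand in for drug. With run-in drug in the model, the mean difference fell to between −0.05 and +0.04 mmHg and rejection to 4.4% to 5.8% in every scenario.

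**What the illustration does not cover.** It suits a DBP-type change with about 108 per subgroup. It was not computed for SBP or for the binary Endpoints 3.3 and 3.4. The Visit 2 comparisons use the Full Analysis Set, and Endpoint 3.2 is limited to patients uncontrolled at Visit 3, so their numbers differ.

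**The case against.** The strongest reply is that the plan does not claim an effect of switching. It defines two pooled groups by prior therapy and says that a small p-value shows a difference between them, which is true whatever the cause. That stands as a matter of wording. A reader might still infer that the SAP attributes the difference to switching; the text does not say so. But the label invites that reading, and an LS-mean difference or odds ratio that mixes prior therapy with drug class is hard to use under either reading.

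Second, the mix may already be visible. The Treatment at Run-In row of Table 14.1.3 has four levels (ZOF 30 mg, AML 5 mg, other ACE inhibitor, other CCB), which appear to record prior therapy and so amount to drug crossed with continued/switched. The Visit 1 to Visit 2 vital-sign table is also split by drug. This lets a reader detect an imbalance in the Safety population. It adjusts none of the estimates or p-values.

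Third, the magnitude is assumed throughout. That stands. A reader might take the 22% as a property of this trial, but the documents give neither the mix nor the drug difference, and no bias at all is among the possibilities. For change from screening to Visits 3 and 4, when everyone is on both drugs, a lasting difference by run-in drug is less obvious than at Visit 2.

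Fourth, adjustment does not make the comparison causal. That also stands: prior agent, prior dose and the act of changing drug would still differ. Finally, extra terms could strain the stratified logistic models, where the SAP already foresees non-convergence. This is a reason to keep the added terms few.

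**Conclusion.** The point holds in conditional form. Run-in drug is missing from every model and fallback for Endpoints 3.1 to 3.4, and the design balances drug only overall. Bias needs both an unequal ZOF/AML mix between the subgroups and a BP change that differs by run-in drug; with either absent it is zero. Under the stated assumptions the false-positive rate lies between 5% and 22%, with spurious differences of 0 to 1.6 mmHg.

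The documents do not support the stronger inference that these comparisons will be biased, or that the trial's main conclusions are at risk. The endpoints are labelled exploratory, and the primary and secondary analyses do not use the continued/switched split. This is a cheap improvement to exploratory analyses. Even after it is made, the results should be read as a non-randomized comparison.

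**What to change.** - Add run-in drug (ZOF 30 mg or AML 5 mg) as a fixed effect in the models for Endpoints 3.1 to 3.4. It can be derived by collapsing the four levels of Treatment at Run-In: ZOF with other ACE inhibitor, AML with other CCB.
- Add drug-by-visit only where a model has more than one post-baseline visit. It cannot be estimated for Endpoint 3.2 or in the Visit 2 monotherapy models of the table shells.
- In the fallbacks, replace the t-test with a linear model containing subgroup, run-in drug and starting BP, and use an odds ratio stratified by run-in drug.
- Tabulate run-in drug by continued/switched in the populations used for these endpoints.

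**Cost.** No new data are needed. The terms use 1 degree of freedom in a single-visit model, 2 in a two-visit model and 3 in the three-visit model of SAP 7.4.1. With 110 per subgroup, the SE is 10 × √(2/110) = 1.35 mmHg. With even subgroups and drugs, it rises by a factor 1/√(1 − ρ²), where ρ is the difference in shares: 1.35/√(1 − 0.2²) = 1.38 at 40/60 and 1.35/√(1 − 0.4²) = 1.47 at 30/70. At equal mix there is essentially no loss.
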